12.4 Technical complaints and technical complaint samples

12.4.1 Reporting of technical complaints

All technical complaints on any of the following products:

- IDegLira, 100 units/mL + 3.6 mg/mL, 3 mL prefilled PDS290 pen injector
- IDeg (Tresiba[®]), 100 units/mL, 3 mL prefilled PDS290 pen injector
- Needles for prefilled pens

which occur from the time of first usage of the product until the time of the last usage of the product, must be collected and reported to Customer Complaint Center, Novo Nordisk. Contact details (fax, e-mail and address) are provided in [Attachment I](#) to the protocol.

The investigator must assess whether the technical complaint is related to any AEs or SAEs.

Technical complaints must be reported on a separate technical complaint form:

- One technical complaint form must be completed for each affected DUN
- If DUN is not available, a technical complaint form for each code or lot number must be completed

The investigator must complete the technical complaint form in the eCRF within the following timelines of the trial site obtaining knowledge of the technical complaint:

- Technical complaint assessed as related to an SAE **within 24 hours**
- All other technical complaints **within 5 calendar days**

If the eCRF is unavailable or when reporting a technical complaint that is not subject related, the information must be provided on a paper form by fax, e-mail or courier to Customer Complaint Center, Novo Nordisk, within the same timelines as stated above. When the eCRF becomes available again, the investigator must enter the information on the technical complaint form in the eCRF.

12.4.2 Collection, storage and shipment of technical complaint samples

The investigator must collect the technical complaint sample and notify the monitor **within 5 calendar days** of obtaining the sample at trial site. The monitor must coordinate the shipment to Customer Complaint Center, Novo Nordisk (the address is provided in [Attachment I](#)) and ensure that the sample is sent as soon as possible. A copy of the technical complaint form must be included in the shipment of the sample. If several samples are returned in one shipment, the individual sample and the corresponding technical complaint form must be clearly separated.

The investigator must ensure that the technical complaint sample contains the batch, code or lot number and, if available, the DUN. All parts of the DUN should be returned.

If the technical complaint sample is unobtainable, the investigator must specify on the technical complaint form why it is unobtainable.

Storage of the technical complaint sample must be done in accordance with the conditions prescribed for the product.

12.5 Pregnancy

12.5.1 Pregnancy in female subjects

Female subjects must be instructed to notify the investigator immediately if they become pregnant during the trial. The investigator must report any pregnancy in subjects who have received trial product(s). The investigator must follow the pregnancy until the pregnancy outcome and the newborn infant is one month of age.

The investigator must report information about the pregnancy, pregnancy outcome, and health of the newborn infant(s), as well as AEs in connection with the pregnancy, and AEs in the foetus and newborn infant.

The following must be collected and reported by the investigator to Novo Nordisk - electronically (e.g. in PDF format), or by fax or courier:

1. Reporting of pregnancy information

Information about the pregnancy and pregnancy outcome/health of the newborn infant(s) has to be reported on Maternal Form 1A and 1B, respectively.

When the pregnancy outcome is abnormal (i.e. congenital anomalies, foetal death including spontaneous abortion and/or any anomalies of the foetus observed at gross examination or during autopsy), and/or when a congenital anomaly is diagnosed within the first month, further information has to be reported for the female subject on Maternal Form 2. In addition, information from the male partner has to be reported on the Paternal Form, after an informed consent has been obtained from the male partner.

Initial reporting and follow-up information must be reported **within 14 calendar days** of the investigator's first knowledge of initial or follow-up information.

2. Reporting of AE information

The investigator has to report AEs in connection with the pregnancy as well as in the foetus and newborn infant(s). The SAEs that must be reported include abnormal outcome, such as foetal death (including spontaneous abortion), and congenital anomalies (including those observed at gross examination or during autopsy of the foetus), as well as other pregnancy complications fulfilling the criteria of an SAE.

Forms and timelines for reporting AEs:

Non-serious AEs:

- AE form^a **within 14 calendar days** of the investigator's first knowledge of the initial or follow-up information to the non-serious AE.

SAEs:

- AE form^a **within 24 hours** of the investigator's first knowledge of the SAE.
- Paper SIF **within 5 calendar days** of the investigator's first knowledge of the SAE.
- **SAE follow-up information** to the AE form and/or SIF **within 24 hours** of the investigator's first knowledge of the follow-up information.

^a It must be clearly stated in the AE diagnosis field on the AE form if the event occurred in the subject, foetus or newborn infant. If the AE occurred in the foetus or newborn infant, the AE can only be reported on paper AE and SIF.

Any queries or follow-up requests from Novo Nordisk to non-serious AEs, SAEs and pregnancy forms must be responded to by the investigator **within 14 calendar days** from the date of receipt of the request, unless otherwise specified in the follow-up request.

12.6 Precautions and/or overdose

Treatment with glucose-lowering agents such as insulin and GLP-1 therapies carry the risk of hypoglycemia.

Symptoms of hypoglycaemia usually occur suddenly and may include cold sweat, nervousness or tremor, anxious feelings, unusual tiredness, confusion, difficulty in concentrating, excessive hunger, temporary vision changes, headache, nausea and palpitation. Severe hypoglycaemia may lead to unconsciousness.

Hypoglycaemic episodes should be treated according to best practise at the discretion of the investigator. Attention should be given to the fact that the action profile of the insulin component in IDegLira and IDeg is flat and of somewhat longer duration than currently marketed long-acting insulin preparations. It may therefore take several hours more before stable normal BG is achieved after a hypoglycaemic episode when comparing to existing long acting insulin analogues.

Symptoms of minor hypoglycaemia should be treated with ingestion of carbohydrate. Severe hypoglycaemia resulting in loss of consciousness must be treated according to best medical practice (e.g. 25mL of 50% dextrose solution given intravenously, or 0.5-1mg of glucagon given subcutaneously or intramuscularly).

From clinical trials and marketed use of liraglutide (Victoza[®]) overdoses up to 40 times the recommended maintenance dose of 1.8 mg (72 mg) outside Japan have been reported. Events

reported included severe nausea and severe vomiting. None of the reports included severe hypoglycaemia. All patients recovered without complications.

When initiating treatment with IDegLira, the subject may in some cases experience loss of fluids/dehydration, due to vomiting, nausea or diarrhoea. It is important to avoid dehydration by drinking plenty of fluids.

For more information, see the current IB version of IDegLira¹¹, IDeg⁸ and liraglutide⁹ or any updates hereof.

12.7 Committees related to safety

12.7.1 Novo Nordisk safety committee

Novo Nordisk will constitute an internal IDegLira safety committee to perform ongoing safety surveillance. The IDegLira safety committee will be informed about the results of continuous ongoing safety surveillance activities for IDegLira and may recommend unblinding of any data for further analysis. In this case an independent ad hoc group will be established in order to maintain the blinding of the trial personnel.

12.7.2 Event adjudication committee

An independent external event adjudication committee (EAC) is established to perform qualitative or quantitative validation of selected AEs according to pre-defined diagnostic criteria. The validation is based on review of pre-defined clinical data related to the specific AE.

The events are reviewed by the EAC in a blinded manner.

The AEs for adjudication are listed in [Table 12-1](#). A full list of AEs for adjudication and rationales for adjudicating these can be found in [Appendix C](#).

Event adjudication will be performed for AEs in randomised subjects including AEs with an onset date during the screening period. Event adjudication will not be performed for AEs in screening failures.

The EAC is composed of permanent members who cover required medical specialities. The EAC members must disclose any potential conflicts of interest and must be independent of Novo Nordisk. The role of the EAC is solely to adjudicate events in a blinded manner. The EACs will have no authorisations to impact on trial conduct, trial protocol or amendments.

The EAC will review translated copies in English of medical documentation received in the adjudication packages (for example X-ray, ECGs, ultrasound images, discharge summaries,

pathology reports, and death certificates). The investigator must provide medical documentation as soon as possible, when they receive the request from Novo Nordisk.

The EAC can evaluate an event not initially reported as an AE for adjudication to be adjudicated. If so then the investigator must provide medical documentation as soon as possible, when they receive the request from Novo Nordisk or the Event Adjudication vendor.

AEs for adjudication must be reported according to section [12.2](#). In addition the specific adjudication form should be completed within 14 calendar days of the investigator's first knowledge of the AE, and all relevant predefined documents provided within 4 weeks according to instructions in the event adjudication site manual.

The assessment made by the EAC will be included in the clinical trial report as well as the assessments made by the investigator. However, the adjudication made by the event adjudication committee, given its independent analysis of each event, will be attributed with greater importance of the two.

13 Case report forms

Novo Nordisk will provide a system for the eCRFs. This system and support services to the system will be provided by an external supplier.

Ensure that all relevant questions are answered, and that no empty data field exists. If a test or an assessment has not been done and will not be available, or if the question is irrelevant (e.g. is not applicable), indicate this according to the data entry instructions.

The following will be provided as paper CRFs:

- Pregnancy forms

The following will be provided as paper CRFs to be used when access to the eCRF is revoked or if the eCRF is unavailable:

- AE forms
- SIFs
- Technical complaint forms (also to be used to report complaints that are not subject related (e.g. discovered at trial site before allocation))

On the paper CRF forms print legibly, using a ballpoint pen. Ensure that all questions are answered, and that no empty data blocks exist. Ensure that no information is recorded outside the data blocks. If a test/assessment has not been done and will not be available, indicate this by writing "ND" (not done) in the appropriate answer field in the CRF. If the question is irrelevant (e.g. is not applicable)

indicate this by writing “NA” (not applicable) in the appropriate answer field. Further guidance can be obtained from the instructions in the CRF.

The investigator must ensure that all information is consistent with the source documentation. By electronically signing the case book in the eCRF, the investigator confirms that the information in the eCRF and related forms is complete and correct.

13.1 Corrections to case report forms

Corrections to the eCRF data may be made by the investigator or the investigator’s delegated staff. An audit trail will be maintained in the eCRF application containing as a minimum: the old and the new data, identification of the person entering the data, date and time of the entry and reason for the correction.

If corrections are made by the investigator’s delegated staff after the date the investigator has signed the case book, the case book must be signed and dated again by the investigator.

Corrections to the data in the paper CRFs should be made by drawing a straight line through the incorrect data and then writing the correct entry next to the data that were crossed out. Each correction must be initialled, dated and explained (if necessary) by the investigator or the investigator’s authorised staff.

13.2 Case report form flow

The investigator must ensure that data is recorded in the eCRF as soon as possible, preferably within **5 days** after the visit. Once data has been entered, it will be available to Novo Nordisk for data verification and validation purposes. Queries will be generated on an ongoing basis and investigator must ensure that queries are resolved as soon as possible, preferable within 5 calendar days.

The SMBG measurements and corresponding trial drug doses for titration purpose should be entered within **24 hours** after the site visit/phone contact throughout the trial.

At the end of trial the investigator should ensure that all remaining data have been entered into the eCRF no later than **3 days** after LPLV at the site in order to ensure the planned lock of the database.

Site specific eCRF data (in an electronic readable format) will be provided to the trial site before access to the eCRF is revoked. This data must be retained at the trial site.

13.2.1 Paper case report form flow

The pregnancy forms are paper based CRFs. Also, the technical complaint form, SIF and AE form will be provided in paper but are only to be used if for any reason the eCRF is unavailable. If corrections are needed, see section [13.1](#).

14 Monitoring procedures

During the course of the trial, the monitor will visit the trial site to ensure that the protocol is adhered to, that all issues have been recorded, to perform source data verification and to monitor drug accountability. The first monitoring visit will be performed as soon as possible after FPFV at the trial site and no later than 4 weeks after. The monitoring visit intervals will depend on the outcome of the remote monitoring of the eCRFs, the trial site's recruitment rate and the compliance of the trial site to the protocol and GCP, but will not exceed 12 weeks until LPLV at the trial site.

The monitor must be given direct access to all source documents (original documents, data and records). Direct access includes permission to examine, analyse, verify and reproduce any record(s) and report(s) that are important to the evaluation of the trial. If the electronic medical record does not have a visible audit trail, the investigator must provide the monitor with signed and dated printouts. In addition the relevant trial site staff should be available for discussions at monitoring visits and between monitoring visits (e.g. by telephone).

All data must be verifiable in source documentation other than the eCRF, except age and BMI which are calculated by the eCRF.

For all data recorded the source document must be defined in a source document agreement at each trial site. There must only be one source defined at any time for any data element.

Considering the electronic source data environment, it is accepted that the earliest practically retainable record should be considered as the location of the source data and therefore the source document.

The diary is considered source document for the SMBG values, trial product dosing information and hypoglycaemic episodes.

Source data generated by the trial site can be corrected by another person than the person entering the source data; any correction must be explained, signed and dated by the person making the correction.

The original completed diaries must not be removed from the trial site, unless they form part of the eCRF and a copy is kept at the site.

The monitor will ensure that the eCRFs are completed on an ongoing basis.

The following data will be source data verified for screening failures:

- Date for obtaining informed consent.
- Reason for screening failure

Monitors will review the subject's medical records and other source data (e.g. the diaries) to ensure consistency and/or identify omissions compared to the eCRF. If discrepancies are found, the investigator must be questioned about these.

A follow-up letter (paper or electronic) will be sent to the investigator following each monitoring visit. This should address any action to be taken.

15 Data management

Data management is the responsibility of Novo Nordisk.

Appropriate measures, including encryption of data files containing person identifiable data, will be used to ensure confidentiality of subject data, when they are transmitted over open networks.

Data from central laboratories will be transferred electronically. In cases where data is transferred via non-secure electronic networks, data will be encrypted during transfer.

The subject and any biological material obtained from the subject will be identified by subject number and trial ID. Appropriate measures such as encryption or leaving out certain identifiers will be enforced to protect the identity of subjects in all presentations and publications as required by local, regional and national requirements.

16 Computerised systems

Novo Nordisk will capture and process clinical data using computerised systems that are described in Novo Nordisk Standard Operating Procedures and IT architecture documentation. The use and control of these systems are documented.

Investigators working on the trial may use their own electronic systems to capture source data.

17 Statistical considerations

Novo Nordisk will analyse and report data from all sites together.

All analyses of efficacy and safety endpoints will be based on the full analysis set (FAS). All efficacy endpoints will be summarised using the FAS and safety endpoints will be summarised using the safety analysis set (SAS).

The impact of protocol deviations and outliers may be investigated further in sensitivity analyses if deemed relevant.

Unless otherwise specified, all continuous measurements will be summarised descriptively at each visit by treatment using observed data. After 26 weeks of treatment, descriptive statistics will be

presented based both on observed and last observation carried forward (LOCF) imputed data. Endpoints that are analysed untransformed and endpoints that are not formally analysed are summarised by the arithmetic mean, standard deviation (SD), median, and minimum and maximum value. Endpoints that are analysed log-transformed are supplemented with the geometric mean and coefficient of variation (CV).

For measurements over time, mean values will be plotted to explore the trajectory over time. LOCF imputed data will be used as the basis for plotting data, if not otherwise specified. For endpoints that are analysed log-transformed, the geometric mean values will be plotted.

A standard analysis of covariance (ANCOVA) model will be applied for the continuous primary and secondary endpoints. The model includes treatment, pre-trial anti-diabetic treatment (metformin + basal insulin, metformin + one other OAD + basal insulin, metformin + pre-mix/combination insulin, metformin + one other OAD + pre-mix/combination insulin) as fixed factors and the corresponding baseline value as covariate. In the following, this model will be referred to as the standard ANCOVA model.

Presentation of results from a statistical analysis will include the estimated mean treatment effects (Least Square Means [LSMeans]) for absolute values and change from baseline. In addition, estimated mean treatment difference (or ratio) will be presented together with the two-sided 95% confidence interval and corresponding two-sided p-value.

Handling of missing data

The expected percentage of missing data is around 15%. In accordance with industry guidance²⁴ endpoints will be assessed at frequent visits. If an assessment has been made both at screening (V1) and randomisation (V2), and if not otherwise specified, the value from the randomisation visit will be used as the baseline value. If the value measured at the randomisation visit is missing and the assessment also has been made at screening, then the screening value will be used as the baseline value.

Missing values (including intermittent missing values) will be imputed using the LOCF method. Subjects without data after randomisation will be included by carrying forward their baseline value. LOCF has been a standard approach in diabetes trials for many years, and was used as the primary analysis in both IDegLira and IDeg phase 3 trials. LOCF is considered to be an appropriate method in the context of treat-to-target trials, where subjects after withdrawal typically continue their therapy using commercially available insulin. In previous treat-to-target trials with IDegLira and IDeg, LOCF has generally provided similar results to alternative methods applied to handle missing data, such as repeated measures models and completer analyses. In this trial, similar sensitivity analyses will be made to examine the robustness of the LOCF method

17.1 Sample size calculation

The primary objective of this trial is to confirm the superiority of insulin IDegLira versus IDeg in controlling glycaemia in Japanese subjects with T2DM. The primary endpoint is the change from baseline in HbA_{1c} after 26 weeks.

Formally, let D be the mean difference (IDegLira - IDeg) in change from baseline in HbA_{1c}. Superiority will thus be considered confirmed if the upper bound of the two-sided 95% confidence interval for D is strictly below 0.0%. Equivalently, if the p-value for the two-sided test of

$$H_0: D = 0 \text{ against } H_A: D \neq 0,$$

is less than 5% and $D < 0$, where D is the mean treatment difference. This is equivalent to using a one-sided test of size 2.5%, which means that the type 1 error rate is controlled at 2.5%.

The sample size is determined using a t-statistic under the assumptions of a two-sided test of size 5%, a mean treatment difference of 0.45% for the completers, a retained effect of 0.2% for the 15% withdrawals and a standard deviation of 1.0%. Superiority will be investigated on the FAS. The above assumptions are based on experience from the phase 3a development programmes for IDegLira and IDeg. From these assumptions and based on a 1:1 randomisation the sample size is set to 105 subjects per treatment arm; in total 210 subjects will be randomized. This will ensure a nominal power of at least 84.5% (see [Table 17-1](#)).

Table 17-1 Power for various rates of withdrawal and efficacy retention (adjusted treatment difference)

Eff.ret.(%)	Withdrawal rate			
	5%	10%	15%	20%
0.00	86.9% (0.428)	83.2% (0.405)	78.8% (0.383)	73.8% (0.360)
0.10	87.7% (0.433)	84.9% (0.415)	81.8% (0.398)	78.2% (0.380)
0.15	88.0% (0.435)	85.7% (0.420)	83.2% (0.405)	80.3% (0.390)
0.20	88.4% (0.438)	86.5% (0.425)	84.5% (0.413)	82.2% (0.400)

Considering 0% efficacy retention as the most conservative approach for the anticipated 15% of subjects discontinuing randomised treatment, for the multiple imputation sensitivity analysis, the expected treatment difference is reduced to 0.38% for the superiority test. A total of 105 subjects per treatment arm will then yield a superiority power of at least 78.8%.

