The estimates and standard deviations for the 1000 data sets are pooled to one estimate and associated standard deviation using Rubin's rule²⁶. From these pooled estimates the confidence interval for the treatment differences and the associated p-value are calculated.

The results of sensitivity analyses will be compared to the result of the standard ANCOVA method using LOCF for imputation of missing data. Any marked difference between the MMRM, the pattern mixture approach and ANCOVA LOCF approach regarding the estimated treatment difference will be commented upon in the clinical trial report.

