2.1 Sample size calculation

Sample size calculations are described in the protocol section 17.1 and will not further be described here.

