2.3.1 Sensitivity analysis

Sensitivity analysis will be performed on FAS using the mixed model for repeated measurement (MMRM) to evaluate the robustness of using LOCF. All HbA_{1c} values available post baseline at scheduled measurement times will be analysed in a linear mixed normal model using an unstructured residual covariance matrix for HbA_{1c} measurements within the same subject. The model will include treatment, visit and pre-trial anti-diabetic treatment as fixed factors and baseline HbA_{1c} as covariate. Interactions between visit and all factors and between visit and baseline HbA_{1c} are also included in the model.

Further, a pattern mixture model approach, mimicking an intention-to-treat scenario will be applied. The imputation in the IDegLira arm will be based on IDeg values. It will be done as follows:

- In the first step intermittent missing values are imputed using a Markov Chain Monte Carlo method, in order to obtain a monotone missing data pattern. This imputation is done for each treatment group separately and 1000 copies of the dataset will be generated.
- In the second step, for each of the 1000 copies of the dataset, an analysis of variance model with treatment and pre-trial anti-diabetic treatment as fixed factors, and baseline HbA_{1c} as covariates is fitted to the change in HbA_{1c} from baseline to 4 weeks (V10) for the comparator group only. The estimated parameters, and their variances, from this model are used to impute missing values at 4 weeks for subjects in comparator and IDegLira treatment groups, based on pre-trial anti-diabetic treatment and HbA_{1c} at baseline.
- In the third step, for each of the 1000 copies of the dataset, missing HbA_{1c} values at 8 weeks (V14) are imputed in the same way as for 4 weeks. Now the imputations are based on an analysis of variance model with the same factors and the HbA_{1c} values at baseline and 4 weeks as covariates, fitted to the comparator group.
- This stepwise procedure is then repeated sequentially over the available planned visits, adding one visit in each step until the last planned visit at 26 weeks (V32)
- For each of the complete data sets, the change from baseline to 26 weeks is analysed using an analysis of variance model with treatment and pre-trial anti-diabetic treatment as fixed factors and baseline HbA_{1c} value as a covariate.

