The estimates and standard deviations for data sets are pooled to one estimate and associated standard deviation using Rubin's rule³. From these pooled estimates the confidence interval for the treatment differences and the associated p-value are calculated.

The results of the sensitivity analyses will be compared to the result of the standard ANCOVA method using LOCF for imputation of missing data. Any marked difference between the MMRM, the pattern mixture approach and ANCOVA LOCF approach regarding the estimated treatment difference will be commented upon in the clinical trial report.

Additional sensitivity analysis will be performed comparing the treatment difference in subjects recruited by one set of criteria compared to ones recruited with updated set of criteria, in order to evaluate the impact of protocol amendment 2 (08-Sep-2016) implemented during recruitment of subjects.

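### Protocol 17.1's power of at least 78.8% for the multiple-imputation sensitivity analysis is a complete-data figure; with Rubin pooling at the stated inputs it is about 74–76%

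*Protocol*

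**What the plan says.** Protocol 17.1 sizes the trial with a t-statistic: two-sided 5% test, difference 0.45 in completers, SD 1.0, 15% withdrawals and 105 subjects per arm. With a retained effect of 0.2 in withdrawals it reports 84.5% nominal power.

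It then turns to the multiple-imputation sensitivity analysis: "Considering 0% efficacy retention as the most conservative approach for the anticipated 15% of subjects discontinuing randomised treatment", it reduces the expected difference to 0.38 and concludes "A total of 105 subjects per treatment arm will then yield a superiority power of at least 78.8" (%). The same 78.8% is the cell of Table 17-1 for 15% withdrawal and zero retention.

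That sensitivity analysis is defined in Protocol 17.3.1 and SAP 2.3.1. Missing IDegLira values are imputed stepwise from models fitted to the IDeg arm, in 1000 copies. From week 8 onward "the imputations are based on an analysis of variance model with the same factors and the HbA_{1c} values at baseline and 4 weeks" as covariates, with one more visit added at each step. At the end "The estimates and standard deviations for the 1000 data sets are pooled to one estimate and associated standard deviation using" Rubin's rule. On power the SAP adds nothing: "Sample size calculations are described in the protocol section 17.1 and will not further be described here".

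**The concern.** Section 17.1 names a specific analysis, chooses its least favourable retention assumption and gives the resulting power as a minimum. A reader will take 78.8% as the worst case for that analysis. But the calculation adjusts only the mean. Rubin's total variance is the within-imputation variance plus a between-imputation part, and nothing in 17.1 allows for the second part.

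What is at stake is how one sensitivity result is read. If the assumed effect is true and withdrawals retain none of it, the chance of a non-significant result is about 24–26% rather than the implied 21%.

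**Working it through.** **Inputs (Protocol 17.1 unless noted).** n = 105 per arm; SD = 1.0, not stated to be raw or residual; two-sided 5%; completer effect 0.45; withdrawal d = 0.15; retention 0. Pooling by Rubin's rule (Protocol 17.3.1, SAP 2.3.1).

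**Step 1: reproduce the plan's figure.**
- Difference: 0.85 × 0.45 = 0.3825.
- SE = √(2 × 1.0² / 105) = 0.1380.
- Noncentral t, 208 df: power 78.78%, the stated 78.8%.
- With retained effect 0.2: 0.85 × 0.45 + 0.15 × 0.2 = 0.4125, power 84.50%, as stated.
- All 16 cells of Table 17-1 reproduce to within 0.1 point with this formula. The table therefore treats all 210 values as observed.

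**Step 2: add the imputation variance.** Take a single visit, with imputation from the comparator arm in both arms.
- Within: W = 2 × SD² / n = 2/105 = 0.01905.
- Between: B = 2 × d × SD² / n = 0.15 × 0.01905 = 0.00286. The draw of the comparator mean is shared by both arms and cancels in the difference.
- Total: T = 1.15 × W = 0.02190, so the pooled SE is 0.1480 against 0.1380.
- True sampling variance of the pooled estimate: 2 × (1 − d) × SD² / n = 0.01619, SD 0.1272. Rubin's SE is larger than this, so the test is conservative.

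**Step 3: analytic power.** With about 179 df the critical value is about 1.973, so rejection needs an estimate beyond 1.973 × 0.1480 = 0.2921.
- With the true sampling SD: Φ((0.3825 − 0.2921) / 0.1272) = Φ(0.711) = 76.1%.
- With Rubin's SE also used as the sampling SD: Φ(0.0904 / 0.1480) = Φ(0.611) = 72.9%.
- Letting W also carry the mixture of completers and withdrawals (T = 1.163 × W) gives 75.7% and 72.5%.

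**Step 4: simulation at SD 1.0 and strict 0% retention.** ANCOVA with four strata and baseline unless noted, Rubin pooling with small-sample df, 100–200 imputations. The documents give no visit correlations or dropout timing, so those are assumed.

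| Setting | Power |
|---|---|
| Single visit, pooled SE 0.152 | 74.4–74.8% |
| Six visits, correlation 0.5–0.9, uniform or late dropout, no benefit in withdrawals at any visit | 74.8–77.1% |
| Six visits, all dropout before week 4, pooled SE 0.152–0.154 | 72.5–73.9% |
| All dropout before week 4, no strata or baseline terms | 73.0–75.6% |
| Control: complete data, same ANCOVA | 78.5% |

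Monte Carlo SE is 0.4–0.9 points. A smaller run of the case with all dropout before week 4 (2,000 trials per setting, Monte Carlo SE about 1 point) gave 71–74%. The control run shows that the loss comes from the imputation, not from the ANCOVA.

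**Step 5: what closes the gap.**
- *Covariate gain.* With all dropout before week 4, residual SD 0.95 gives 77.6–78.7% and 0.92 gives 80.3–81.7%. If 1.0 is a raw SD, these need covariates explaining 1 − 0.95² = 9.8% and 1 − 0.92² = 15.4% of the variance.
- *Benefit before leaving.* Suppose withdrawals follow an assumed build-up (30, 60, 80, 95, 100 and 100% of the effect over six visits) until they leave. Conditioning on their own earlier values then raises the mean difference to 0.40–0.43, and power to 80–81% for uniform and 83–86% for late dropout.

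**The case against.** The strongest reply is that the method is disclosed. Section 17.1 says that it uses a t-statistic, calls the 84.5% nominal and shows 78.8% as a table cell. *Most conservative* describes the retention assumption, and no Rubin-based calculation is claimed. That is fair, but the sentence still attaches a minimum to the imputation analysis, and the minimum does not follow from the stated inputs.

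Two further replies limit the scope, and both stand. If SD 1.0 is a raw SD, a modest covariate gain restores the figure. And strict 0% retention needs either that all withdrawals leave before the first post-baseline HbA1c at week 4, or that IDegLira withdrawals show no benefit before leaving. Otherwise the algorithm keeps some effect.

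Three stronger readings are tempting, and the documents do not support them.
- *The analysis as run will fall below 78.8%.* That depends on dropout timing, which the documents do not give. Withdrawal criterion 9 in Protocol 6.3 has glucose limits that tighten at weeks 7 and 13, so some withdrawals may well come later.
- *Early gastrointestinal dropout makes 0% retention likely.* Protocol 12.6 says "When initiating treatment with IDegLira, the subject may in some cases experience loss of fluids/dehydration, due to vomiting, nausea or diarrhoea", but gives no withdrawal rate. The rule in Protocol section 17 that "Subjects without data after randomisation will be included by carrying forward their baseline value" says how such subjects are handled, not how many there will be.
- *The trial is underpowered or its conclusion is at risk.* Superiority is concluded from the LOCF ANCOVA on the full analysis set alone (Protocol 17.3, SAP 2.3). The sensitivity analyses are compared on estimates: "Any marked difference between the MMRM, the pattern mixture approach and ANCOVA LOCF approach regarding the estimated treatment difference" is to be commented on in the report, and no significance criterion is set for them.

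**Conclusion.** The point holds as a minor correction. The stated 78.8% is complete-data power. For the analysis it is attached to, with SD 1.0 as the residual SD, 15% withdrawal and 0% retention, power is about 73–77%, best estimate 74–76%, which is about 3–5 points lower.

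The direction is certain, because Rubin pooling adds variance that 17.1 leaves out. The exact size rests on assumed visit correlations and dropout patterns. The shortfall belongs to the 0% retention scenario that 17.1 itself chose. It disappears with a residual SD of about 0.95 or less, or with enough benefit before withdrawal. The difference of 0.38 remains a sound lower planning bound.

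**What to change.** In Protocol 17.1, replace the clause giving at least 78.8% with wording such as: *78.8% for complete data, before imputation variance; about 74–76% with Rubin pooling at residual SD 1.0 and 0% retention*. Add one sentence saying that 0.38 is a lower planning bound, because the retention produced by the specified imputation depends on when subjects withdraw. It would also help to say whether SD 1.0 is raw or residual.

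SAP 2.1 follows by reference, and SAP section 3 could record the clarification. The cost is wording only, plus a slightly less favourable stated power for one sensitivity analysis. Sample size, primary analysis, the 84.5% figure and the imputation algorithm do not change.
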